Potential subjects may also be referred to the study by their physician either at the host VAMC or academic affiliate. The study will use an approved flyer as advertisement. Potential subjects may contact study staff by phone to determine eligibility or to inquire more about the study. Staff will respond to phone inquiries from patients who self-identify as interested, explain the study, and pre-screen them for eligibility. Those who qualify

preliminarily will be scheduled for a full evaluation and will be mailed an advance copy of the consent form along with a “first appointment letter.” Informed Consent discussion will be conducted during the first visit and if the potential participant consents to participate in the study they will be further evaluated clinically for eligibility based on specific inclusion/exclusion criteria per study protocol.

[figure not shown]
Inclusion criteria:

- Clinical diagnosis of PD determined by a board-certified neurologist with specialty training in movement disorders
- An ICIQ-OAB Symptom Score of ≥ 7 , which indicates clinically significant symptoms of OAB, defined as *presence of urinary urgency with or without urgency incontinence usually with increased daytime frequency and nocturia in the absence of infection or other obvious pathology*^{32,35}.

Exclusion criteria:

- Significant cognitive impairment, as indicated by a Montreal Cognitive Assessment³⁶ (MoCA) score of < 18 (or < 14 for the MoCA Blind), which is the recommended diagnostic cutpoint for dementia in PD³⁷.
- Previous intensive pelvic floor muscle exercise training
- Clinically significant depression as measured by a Geriatric Depression Scale-Short Form³⁸ score ≥ 10 which could affect motivation to fully engage in the intervention
- Use of an indwelling urinary catheter
- Post-void residual (PVR) urine measurement by bladder ultrasound of ≥ 150 mL
- Severe uterine prolapse past the vaginal introitus
- Poorly controlled diabetes defined by a hemoglobin A1c (HgbA1c) of $>9.0\%$ within the last 3 months. Participants with poorly controlled diabetes will be offered enrollment if the OAB symptoms persist after improvement in diabetes control
- Chronic renal failure and on hemodialysis
- Genitourinary cancer with ongoing surgical or external beam radiation treatment
- Previous artificial urinary sphincter, sling procedure or implanted sacral neuromodulation device
- History of bladder-injection of botulinum toxin in the last 12 months

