Randomization: At the second visit, eligible participants will be randomized to one of two groups: treatment with PFME-based behavioral therapy or solifenacin drug therapy. Participants will be stratified by site, gender, UI severity (< or \geq a score of 9 on the ICIQ-OAB), and PD motor symptom severity (MDS-UPDRS < 33 on the part 3 motor score)⁵⁹. Participants will be randomized through computer-generated block randomization in groups of six. Based on preliminary data showing these cut points approximate the means among our randomized participants, we do not anticipate four stratification variables will present a challenge to recruitment. While participants will not be blinded to treatment group, the interventionist will be blinded to the participant's performance on the neuropsychological tests and SRTT performance.

Data Management: Participants' assessment data will be kept in a locked cabinet behind a locked door at each site of the Birmingham/Atlanta GRECC and the Richmond PADRECC. Bladder diaries will be scored by a research assistant who is blinded to the assigned treatment group. Data from the Birmingham and Richmond sites will be uploaded to a secure VA server in the form of PDF documents scanned on a VA device behind the VA firewall. Deidentified data will be entered and verified in Redcap by research staff at the Atlanta site, which will ensure accuracy of the data. A standard form will be used to record the date and reason for all

exclusions and dropouts, and these data will also be entered into the master database. Four times per year the PI will meet with the Atlanta-based data manager to review accrual, data entry, and eligibility criteria and examine the database for outliers or database entry errors at each site. The Redcap database will then be converted and data analyses will be completed in SAS 9.4 (SAS Institute, Cary, NC). Additional details regarding confidentiality of patient data are included in the Human Subjects plan.

Specific Aim #1: Using a RCT, determine non-inferiority of pelvic floor muscle exercise-based behavioral therapy versus drug therapy for urinary symptoms in PD.

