Power Analysis: The power analysis is informed by the ICIQ-OAB symptom score reduction observed in the BETTUR PD and BETTUR2 studies of behavioral therapy for urinary symptoms in PD. Based upon the bladder diary-derived UI frequency data (consistent measure used in both behavioral and drug trials), the effect of behavioral therapy and drug therapy to reduce UI frequency is similar. The ICIQ-OAB symptom score range is 0-16, with higher scores indicating worse symptoms. A score \geq 7 would indicate clinically significant OAB symptoms (urgency, frequency, urgency UI, nocturia) occurring on average at least *sometimes*. In our previous studies, we have observed a 2-3 point reduction in the symptom score, which represents a 12%-19% reduction from baseline^{24,64}. The minimally clinically important difference for the ICIQ-OAB is defined as a statistically significant reduction in the symptom score that is accompanied by a reduction in bother and improvement in OAB-specific QOL. Because the observed reduction **\geq 2 points** represents a statistically and clinically meaningful difference, we propose a non-inferiority margin of 15%. Thus, we will randomize 90 participants in order to complete the interventions in 80 participants, which assumes 85% power and a non-inferiority margin on the OAB symptom score of 15% at 12-weeks post-randomization. **Table 6 indicates that the proposed sample size will permit an assessment of non-inferiority within a range of potential non-inferiority margins that correspond to outcome assessments in our pilot studies.**

Standard Deviation of 12 week ICIQ-OAB Symptom Score	Margin of Non-Inferiority Between Groups at 12 weeks (Assumes OAB Symptom Score at baseline of = 8.1)				
	10%	12.5%	15%	20%	
	1.0	23	16	11	7
2.0	89	59	40	24	
3.0	198	131	88	52	

Table 7: Summary Outcome Assessments

Outcome Assessment	Baseline Visit 1/Visit 2	2 weeks Visit 3	4 weeks Visit 4	6 weeks Visit 5	8 weeks Visit 6	12 weeks Visit 7
ICIQ-OAB	X			X		X
7-day Bladder Diary (drug)	X			X		X
7-day Bladder Diary (behavioral)	X	X		X		X
7-day PFME Record (behavioral)		X				
ICIQ-OAB QOL	X			X		X
Benefit & Satisfaction				X		X
Life Space Assessment	X			X		X
Self Efficacy for Chronic Disease Management	X					X
Patient Global Symptom Control Score				X		X
Adverse Event checklist	X	X	X	X	X	X
Adherence Questionnaire		X		X		X
Neuropsychological battery	X					X
MDS-UPDRS	X					X

Data Analysis:

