Primary Outcome for Aim 1: To evaluate the impact of treatment within group, we will first use a random effects mixed model with adjustment for baseline OAB symptom severity to compare mean ICIQ-OAB symptom scores across the three time points. In order to test for non-inferiority of behavioral therapy compared to drug therapy, we will assess the difference in the mean 12-week post-randomization ICIQ-OAB symptom score between groups using a two-sample t-test, assuming a non-inferiority margin of 15% and a standard deviation of 2.0 points. The significance level of the test will be set at an α of 0.025 for a one-sided test of significance.

Secondary Outcomes: The pre-treatment and post-treatment frequency of UI based on the bladder diary will be used to calculate a percentage change for each participant ($[\text{pre-treatment frequency} - \text{post-treatment frequency}] / [\text{pre-treatment frequency}] \times 100\%$). Based on pilot study results, non-normality of the diary data is anticipated and thus the Wilcoxon rank sum test will be used for bladder diary-reported outcomes (UI, urgency, nocturia). Questionnaire-based secondary outcomes (ICIQ-OAB bother score, ICIQ-QOL, benefit and satisfaction, self-efficacy, voided volume, and the Life Space Assessment) will be assessed between groups using a t-test. Twenty-four hour voided volume measures will permit an evaluation of nocturnal urine production as a confounding factor for response to treatment among persons with nocturia. Nocturnal urine production includes the sum of all voided volumes after going to bed with the intention of sleeping and the subsequent first voided volume the next morning. Additionally, an evaluation of change in mean voided volume provides an objective measure of functional bladder capacity.

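### The t-test that decides non-inferiority ignores the baseline score and the stratification factors: valid and slightly conservative, but it gives up power if baseline predicts the 12-week score

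*Combined protocol and SAP*

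**What the plan says.** Data Analysis, Primary Outcome for Aim 1, contains two analyses of the ICIQ-OAB score.

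- The first opens with its purpose, "To evaluate the impact of treatment within group", and continues: "we will first use a random effects mixed model with adjustment for baseline OAB symptom severity to compare mean ICIQ-OAB symptom scores" over the three time points.
- The second decides non-inferiority: "we will assess the difference in the mean 12-week post-randomization ICIQ-OAB symptom score between groups using a two-sample t-test". It assumes a margin of 15% and an SD of 2.0, and "The significance level of the test will be set at an α of 0.025 for a one-sided test of significance". It names no covariate.

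The Randomization section says "Participants will be stratified by site, gender, UI severity" (ICIQ-OAB cut at 9) and motor severity (MDS-UPDRS part 3 cut at 33), and "Participants will be randomized through computer-generated block randomization in groups of six".

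Table 6 in the Power Analysis is indexed by "Standard Deviation of 12 week ICIQ-OAB Symptom Score". The sample size therefore rests on the raw SD, as the t-test does. Entry requires "An ICIQ-OAB Symptom Score of ≥ 7".

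**The concern.** The plan treats baseline severity as important enough to stratify on and to adjust for in a preliminary model, then leaves it out of the one comparison that decides Aim 1. Stratifying on a predictive factor makes the arms more alike than chance would. An unadjusted t-test does not credit this, so its standard error is somewhat too large for the design.

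The error is in the safe direction: a false claim of non-inferiority does not become more likely. The cost is a wider interval, so a behavioral therapy that truly is non-inferior is missed more often than necessary.

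The mixed model cannot simply be read as the adjusted primary test. Its stated aim is change within group, and its three time points include baseline, for which it also adjusts. The t-test also drops anyone with a week-6 score but no 12-week score.

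**Working it through.** **Inputs from the documents.** 90 randomized and 80 completers, so 40 per arm (Power Analysis; Human Subjects). Baseline mean 8.1 (Table 6), so the margin is 0.15 × 8.1 = 1.215 points. SD 2.0, one-sided alpha 0.025 (Primary Outcome for Aim 1). Four stratification factors with three sites: 3 × 2 × 2 × 2 = 24 strata, blocks of six.

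**Assumptions.** True difference 0. The correlation r between baseline and 12-week score is not in the documents and is varied.

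**The plan's own figure.** The standard error of the difference is 2.0 × √(2/40) = 0.447, and 1.215/0.447 = 2.72. By noncentral t, power at 40 per arm is 76.5% at one-sided 0.025 and 85.3% at one-sided 0.05. The stated 85% with 40 per arm reproduces only at 0.05. With margins rounded to 0.81, 1.0, 1.22 and 1.6, one-sided 0.05 returns all 12 cells of Table 6. At 0.025, 85% power needs 50 per arm. This is a separate discrepancy. Here it only fixes the starting point at about 76.5%.

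**Closed form with adjustment.** The residual SD is 2.0 × √(1 − r²):

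| r | Residual SD | Power at 40 per arm |
|---|---|---|
| 0 | 2.000 | 76.5% |
| 0.3 | 1.908 | 80.3% |
| 0.5 | 1.732 | 87.3% |
| 0.6 | 1.600 | 91.8% |

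This ignores the degrees of freedom spent on covariates and the effect of stratification, so the design was simulated.

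**Simulation.** 12,000 replicates per cell (Monte Carlo SE about 0.004 for power and 0.0014 for error), 80 analyzed, permuted blocks of six within 24 strata. Further assumptions: integer baseline 7 to 16 with decreasing frequencies and mean 8.1 or 9.0; 25% women; sites 40/35/25%; motor score, gender and site unrelated to outcome. The ANCOVA fits arm, baseline, motor score, gender and two site terms. Each cell gives mean 8.1 / mean 9.0.

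| r | Power, t-test (%) | Power, ANCOVA (%) | One-sided error, t-test |
|---|---|---|---|
| 0 | 76.5 / 76.7 | 75.1 / 75.2 | 0.0246 / 0.0268 |
| 0.1 | 77.1 / 76.5 | 76.1 / 75.3 | 0.0239 / 0.0262 |
| 0.2 | 76.1 / 76.3 | 76.2 / 76.2 | 0.0227 / 0.0237 |
| 0.3 | 77.1 / 76.2 | 79.1 / 78.6 | 0.0216 / 0.0225 |
| 0.4 | 76.8 / 77.3 | 81.8 / 81.9 | 0.0216 / 0.0208 |
| 0.5 | 77.3 / 77.9 | 85.9 / 86.2 | 0.0211 / 0.0222 |
| 0.6 | 78.2 / 78.5 | 91.0 / 91.3 | 0.0168 / 0.0166 |

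ANCOVA error ranged from 0.0223 to 0.0272.

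**Second simulation.** With normal scores, cuts at the median and equal sites, the result is similar. Power for t-test v adjusted is 76% v 78% at r = 0.3 and 78% v 86% at r = 0.5. T-test error is 0.021 and 0.018. Under simple randomization at r = 0.5 the t-test error is 0.024, so the conservatism comes from stratifying without adjusting.

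**Week-6 scores.** If k extra participants per arm have week 6 but not week 12, the variance of an arm mean is s² × [(1 − ρ²)/40 + ρ²/(40 + k)], where ρ is the partial correlation of weeks 6 and 12. With k = 2.5 or 5 and ρ from 0.5 to 0.7, closed-form power rises from 80.2% to 80.8-82.4% at r = 0.3, and from 87.2% to 87.7-88.9% at r = 0.5. That is about 0.5 to 2 points.

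**The case against.** The strongest reply is that this is a preference for efficiency and not a defect. The t-test is prespecified, valid, consistent with the SD used for sample size, and errs on the safe side. That is conceded in full.

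The second reply is that the gain rests on an unknown correlation, and the entry floor narrows the baseline range. A baseline on 7 to 16 with mean 8.1 and decreasing frequencies has an SD of about 1.5. Then r = 0.5 needs 0.5 × 2.0/1.5 = 0.67 week-12 points per baseline point, which is steep. At mean 9.0 (SD about 2.2) it needs 0.5 × 2.0/2.2 = 0.45. This stands: a large gain is possible but not established.

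The third is that the simulation makes motor score, gender and site unrelated to outcome, and so shows only their cost. A check with 4,000 replicates gives t-test, baseline-only and four-factor power of 77.9, 77.3 and 76.4% at r = 0, and 78.6, 87.1 and 86.0% at r = 0.5. The extra terms cost about 1 point when they predict nothing. If motor score explains a further 10% of variance, they repay it: the second simulation gives 76.5% v 77.7% at r = 0 and 78.1% v 89.1% at r = 0.5. Including the factors used in randomization is reasonable, but most of the benefit comes from the baseline score.

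Smaller points also stand. The Human Subjects section names a fourth site, which would make 32 strata, but the result hardly moves (77.3% v 85.7% at r = 0.5). With 90/24 = 3.75 participants per stratum, blocks of six rarely fill, which limits the conservatism. Participants who stop the drug may stay for data collection, so the week-6 gain may be smaller still.

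**Conclusion.** The point holds, as an improvement that should be made and not as a flaw that invalidates the test. Non-inferiority is decided by a comparison that uses neither the baseline score nor any stratification factor. Its one-sided error is at or slightly below 0.025 (0.021 to 0.024 for r of 0.2 to 0.5, about 0.017 at 0.6).

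Against the four-factor model, the t-test is about 1 to 1.5 power points better when r is 0 to 0.1 and level near 0.2. It is about 2 points worse at 0.3, 5 at 0.4, 8 at 0.5 and 13 at 0.6. The sizes depend on an assumed r, a margin of 1.215 points, SD 2.0 and 80 completers, so confidence in the gain is moderate. Adjustment does not resolve the mismatch between the stated 85% power and alpha 0.025. By the closed form it would reach 85% at 40 per arm only if r is about 0.45 or more.

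**What to change.** Before outcome data are seen, specify the primary non-inferiority test as the week-12 between-arm contrast from a baseline-adjusted model. Either of these would do:

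- an ANCOVA of the 12-week score; or
- a mixed model with weeks 6 and 12 as outcomes, which keeps dropouts who have a week-6 score.

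Include main effects for arm, continuous baseline ICIQ-OAB, MDS-UPDRS part 3, gender and site. Baseline should be a covariate only, and not also an outcome time point. Estimate the variance from the data. Declare non-inferiority if the upper limit of the two-sided 95% confidence interval for behavioral minus drug lies below the margin stated in points. Keep the t-test as a sensitivity analysis. For clarity, move the SD of 2.0 to the sample-size section.

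The cost is SAP wording and a few lines of SAS, with no new data. The model uses about five degrees of freedom with three sites, and a rule for pooling small gender or site cells may be needed. If the correlation proves to be about 0.2 or less there is no gain, and at most about 1.5 points of power are lost.

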We propose a three-site, RCT conducted at the Atlanta (lead site), Birmingham and Richmond VA medical centers to establish non-inferiority of pelvic floor muscle exercise-based behavioral therapy compared to drug therapy for urinary symptoms in adults with PD. Groups will be stratified by OAB symptom severity, PD motor symptom severity, gender, and site. We will randomize 90 participants in order to complete the study in 80 participants, assuming 85% power and a non-inferiority margin for the OAB symptom score of 15% at 12-weeks. **The primary outcome measure will be urinary symptom severity as measured by the ICIQ-OAB symptom score^{32,33}** collected at 3 time points during the study: baseline, 6 weeks, and 12 weeks. PFME-based behavioral therapy will occur over 3 visits conducted during the first 6 weeks as was performed in the BETTER2 PD study. Participants in the drug therapy group will also have 3 visits during the first 6 weeks in order to individually titrate solifenacin drug therapy according to a validated symptom scale. Solifenacin has been selected because this bladder-selective anticholinergic drug (less risk of cognitive side effects) is the only drug with published evidence of potential efficacy in PD³⁴. At baseline, randomized participants will undergo a brief neuropsychological battery adapted from our current study to assess cognitive factors that may predict a preferred treatment strategy. At the 12-week assessment, the brief neuropsychological battery and MDS-UPDRS will be repeated in order to assess any change associated with treatment allocation. Follow-up visits will occur at weeks 4 and 8 to ascertain side effects and assess treatment adherence.

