Human Subjects Involvement and Characteristics: Men and women with PD recruited from the Atlanta, Birmingham, Richmond, and Philadelphia VAMCs as well as in the surrounding community. We propose randomizing 90 participants to either exercise-based behavioral therapy or drug therapy with Solifenacain. In order to complete the study in 80 participants, we anticipated having to screen approximately 180 PD patients to identify those with clinically significant OAB symptoms, and enroll approximately 45 participants in each group. These estimates are based on our experiences in the BETTUR PD and BETTUR2 pilot studies. In the BETTUR PD study, 33 individuals were screened to enroll 20 participants. Of the 20 participants who were enrolled, 17 completed the study demonstrating a 15% drop out rate once enrolled. To date, in the BETTUR2 study, we have screened 107 individuals to randomize 51 participants and have had 6 participants drop out (11.7% rate).

During FY16, 541 unique Veterans with PD were served by the Atlanta VA and surrounding CBOCs. For the BETTUR PD pilot, 14 of the 32 screened subjects were recruited from the Atlanta VA after mailing letters to 360 Veterans identified with a diagnosis of PD in the Metro Atlanta area in FY08. Recruitment was extended to a university-based movement disorders clinic to achieve the intended sample size of 20 enrolled subjects. For the BETTUR2 study, of the 65 persons who have undergone screening procedures thus far, 25 were Veterans and 40 were recruited from university-based movement disorders clinics in Atlanta and Birmingham in order to maximize the team's ability to recruit the intended sample size. Thus, we propose to recruit both Veterans and non-Veterans for the proposed study from the outset. The university affiliates in Atlanta (Emory), Birmingham (University of Alabama at Birmingham), Richmond (Virginia Commonwealth University), Philadelphia (University of Pennsylvania) all have active movement disorders programs, which enhance the overall resources available to the study.

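### The deciding non-inferiority t-test uses only participants with a week-12 score, although about 11% dropout is planned for and the baseline and week-6 scores go unused; the direction of any bias is unknown.

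*Combined protocol and SAP*

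**What the plan says.** All references are to the combined protocol and SAP.

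- **Deciding test** (Data Analysis, Primary Outcome for Aim 1): "we will assess the difference in the mean 12-week post-randomization ICIQ-OAB symptom score between groups using a two-sample t-test". The planning values for this test are given as "assuming a non-inferiority margin of 15% and a standard deviation of 2.0 points". The level follows: "The significance level of the test will be set at an α of 0.025 for a one-sided test of significance". No covariate enters this test.
- **Mixed model** (same paragraph): a random-effects model adjusted for baseline severity is planned over the three time points, but its stated purpose is the effect of treatment within each group.
- **Expected loss**: Research Design and Methods states "We will randomize 90 participants in order to complete the study in 80 participants". Power Analysis words it as "we will randomize 90 participants in order to complete the interventions in 80 participants, which assumes 85% power". Human Subjects Involvement and Characteristics reports that in the first pilot "17 completed the study demonstrating a 15% drop out rate once enrolled", and that 6 of 51 had dropped out of the second pilot so far (printed as 11.7%).
- **Data available**: Table 7 schedules the ICIQ-OAB at baseline, week 6 and week 12.
- **Follow-up after stopping treatment** (Drug Intervention: Solifenacin): a participant who stops the drug may stay in the study solely to provide data. No matching offer is written for the behavioral arm.
- **Dropout records** (Data Management): the date and reason of each dropout are recorded, but no analysis rule uses them.

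Nowhere is an intention-to-treat or per-protocol population named, nor a missing-data method or sensitivity analysis for the primary outcome.

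**The concern.** A t-test on week-12 scores needs a week-12 score. Without an imputation rule, a participant who lacks one drops out of the primary comparison even if a week-6 score is on file. In a non-inferiority trial this matters because excluding people is not automatically the cautious choice. If those who leave the behavioral arm are mainly the ones it did not help, the remaining participants look better than the arm as randomized, and the test can pass too easily. Participants know their treatment (Randomization section) and report the primary outcome themselves, so leaving because of perceived lack of benefit is plausible in either arm. The trial is meant to inform treatment guidelines, so a false non-inferiority claim would have consequences. The plan also gives no pre-specified answer to the question of who is in the primary analysis.

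**Working it through.** **Inputs from the documents.** One-sided level 0.025, SD 2.0 and margin 15% (Primary Outcome for Aim 1). Table 6 states "Assumes OAB Symptom Score at baseline of = 8.1", which gives a margin of 0.15 × 8.1 = 1.215 points. About 45 are randomized per arm. Previous benefit was 2-3 points (Power Analysis).

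**The plan's attrition figure.** (90 − 80)/90 = 11.1%, and 80/(1 − 0.111) = 90, so the step reproduces. The pilots give 3/20 = 15% and 6/51 = 11.8%. At 15% loss, 90 × 0.85 = 76.5 would complete.

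**The plan's 40 per group (Table 6).** This does not reproduce at one-sided 0.025 with 85% power, which needs 49 per group (50 with the exact t distribution). It reproduces at one-sided 0.05 (39, or 40 exact). That is a separate matter and does not affect the check below.

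**Method.** Set the true difference in all randomized participants (behavioral minus drug, higher is worse) equal to the margin. Let p be the share missing in an arm and g the mean week-12 score of its missing participants minus that of its observed participants.

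- Bias in favor of behavioral therapy = p_B × g_B − p_D × g_D
- SE = 2.0 × √(1/n_B + 1/n_D), with n the number observed
- False non-inferiority rate = Φ(−1.96 + bias/SE)

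**The gap g is an assumption**, because the documents give no week-12 scores for dropouts. A range consistent with the null can be built from the plan's own benefit. If the drug gives 2-3 points and behavioral therapy is truly 1.215 worse, the behavioral arm's mean benefit is 2 − 1.215 = 0.785 to 3 − 1.215 = 1.785. If its dropouts end with zero benefit, its completers average that value divided by (1 − p):

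- 11.1% loss: 0.785/0.889 = 0.88 to 1.785/0.889 = 2.01
- 15% loss: 0.785/0.85 = 0.92 to 1.785/0.85 = 2.10

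These are the gaps g_B.

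**Results.**

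| Case | Bias (points) | SE | False non-inferiority rate |
|---|---|---|---|
| 11.1% missing in both arms, same gap in both | 0 | 0.447 | 2.5% |
| 3/45 behavioral and 7/45 drug missing, both 2 points worse | 2 × (3 − 7)/45 = −0.178 | 0.448 | Φ(−2.36) = 0.9% |
| 7/45 behavioral and 3/45 drug missing, both 2 points worse | +0.178 | 0.448 | Φ(−1.56) = about 6% |
| 11.1% in both arms, behavioral dropouts with zero benefit, drug dropouts like completers | 0.111 × 0.88 = 0.098 to 0.111 × 2.01 = 0.223 | 0.447 | Φ(−1.74) = 4% to Φ(−1.46) = 7% |
| 15% in both arms, same pattern | 0.15 × 0.92 = 0.139 to 0.15 × 2.10 = 0.315 | 0.457 | Φ(−1.66) = 5% to Φ(−1.27) = 10% |

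Simulating the t-test itself (40,000 trials per case) agrees: 2.5% with a 2-point gap in both arms at 11.1% loss, 7.2% with a 2-point gap in the behavioral arm only, and 0.9% and 5.8% for the two unequal-loss cases.

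**The case against.** **The plan is silent rather than wrong.** A t-test does not itself prescribe how missing values are treated, so a reader who infers that the plan adopts a completers-only rule goes too far. What stands is that no other rule is given, and the stated test cannot use a person without a week-12 score.

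**The 11% need not all be missing scores.** Power Analysis speaks of completing the interventions, and someone who stops the drug may still supply a week-12 questionnaire. This is fair, so 11% should be read as anticipated dropout and not as a minimum missing share. Research Design and Methods (completing the study) and the pilot dropout figures make it a reasonable working value.

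**The bias may run the other way.** The documents give reasons for drug-arm loss: adverse events leading to discontinuation, and non-adherence as a route to treatment failure. Potential Risks describes behavioral therapy as free of side effects. Nothing shows heavier or more informative behavioral dropout. This stands, and a reader who infers that the test is known to be biased toward non-inferiority goes beyond the text.

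**Larger error rates can be computed.** A 3-point gap in the behavioral arm alone gives about 11% error at 11.1% loss and 16% at 15%. It is tempting to anchor that gap in the 2-3 point pilot benefit, but it does not fit the null. With a behavioral benefit of only 0.785-1.785 points, it needs dropouts to end about 0.8-1.9 points worse than baseline, or a larger drug benefit than the plan cites.

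**Conclusion.** The point holds as a weakness in the choice of primary analysis. The deciding test discards available baseline and week-6 scores and has no stated treatment of missing week-12 scores, in a trial that plans for about 11% dropout. The effect on the one-sided error is not fixed in sign. In the cases examined it runs from about 0.9%, through no change at 2.5%, to about 4-7% at 11% loss or 5-10% at 15% in the adverse case. Those figures rest on a margin of 1.215 points, SD 2.0, 45 randomized per arm and a drug benefit of 2-3 points. The adverse case also assumes that behavioral dropouts keep no benefit while drug dropouts resemble completers. The documents neither establish nor exclude that pattern, so they support saying that the test can mislead, not that it will.

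**What to change.** In Data Analysis, Primary Outcome for Aim 1:

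1. Replace the t-test as the deciding analysis. Take the week-12 between-group difference and its one-sided 97.5% confidence limit from the mixed model already planned, with week-6 and week-12 ICIQ-OAB as outcomes and baseline as a covariate.
2. Define the population as all randomized participants with any post-baseline ICIQ-OAB score, analyzed as randomized. Include week-12 scores from participants who stopped treatment.
3. State the limits. The model relies on missing-at-random, so it removes outcome-related bias only as far as the observed scores predict it, and it does not recover people who leave before week 6. The plan does not say how many that might be.
4. Add one sensitivity analysis that imputes missing behavioral-arm week-12 scores as progressively worse, for example up to and beyond the margin. Report the point at which the conclusion changes.

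The cost is SAP wording and a little more analysis, with no new participants. The downside is that the result may have to be reported as less robust if it depends on the dropouts. Collecting the week-12 questionnaire by phone or mail from those who miss Visit 7 would reduce the problem at source, but it is an optional added procedure that this fix does not need.
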